6.2 Study Population

Refer to the Core SAP for TLF contents.

6.2.1 Analysis Sets

The frequency table of analysis sets described in Section 4.1 displays results by treatment group (as-randomized for the full, efficacy and migraine analysis sets; as-treated for the safety and follow-up safety analysis sets), not randomized, and overall.

The by-subject listing of analysis sets is provided for the enrolled analysis set.

The administrative listing of randomization scheme and codes is provided for the full analysis set.

6.2.2 Enrollment

The frequency table of enrollment by country and site is provided for the enrolled analysis set, and also displays results for the full and DBT safety analysis sets.

6.2.3 Subject Disposition

The by-subject listing of subject discontinuation is provided for the enrolled analysis set and displays a separate record for each study phase (i.e., DBT, OLE and Follow-Up) that is discontinued (i.e., completed or not completed) corresponding to each type of subject status CRF. The listing includes the following:

- Relevant reference dates: last contact date*, IWRS randomization date
- Study phase: DBT, OLE, or Follow-Up. For each study phase:
 - Last visit date. Derived from visit dates from the Visit Date and Unscheduled Visit Checklist CRFs as follows:
 - DBT Phase: latest visit date in the pretreatment or on-DBT safety analysis period
 - OLE Phase: latest visit date in the OL rimegepant safety analysis period
 - Follow-Up Phase: latest visit date in the follow-up safety analysis period
 - O Phase completion status: "completed"; or "not completed" concatenated with the reason for noncompletion (see Sections 6.2.3.1, 6.2.3.2, 6.2.3.3, 6.2.3.4, and 6.2.3.5)
 - Next phase continuation status: "continued" concatenated with the name of the next phase (OLE or Follow-Up); or "not continued" concatenated with the reason for noncontinuation (see Sections 6.2.3.2, 6.2.3.3, and 6.2.3.4). This does not apply to the Follow-Up Phase.

A footnote describes the derivation of the last contact date as "* Derived as the death date (if it exists); otherwise, the maximum date collected across study population, efficacy safety, and outcomes research parameters". See Section 7.1 for derived dates and Section 7.2 for analysis periods.

6.2.3.1 Subject Disposition From Enrollment to Randomization

The frequency table of subject disposition from enrollment to randomization is provided for the enrolled analysis set based on the DB Subject Status CRF, and displays the following categories:

- Randomized (identified as subjects with nonmissing IWRS randomization date)
- Not randomized (identified as subjects with missing IWRS randomization date)
 - Reasons for discontinuation (i.e., not completing the DBT Phase), including not reported.
 For subjects whose reason is screen failure due to inclusion/exclusion criteria, the reasons for screen failure from the Inclusion/Exclusion CRF are also displayed as subcategories.

6.2.3.2 Subject Disposition From Randomization to Treatment

The frequency table of subject disposition from randomization to treatment is provided by treatment group and overall for the full analysis set based on the DB Subject Status CRF, and displays the following categories:

- Treated with study drug (identified as subjects with nonmissing study drug start date)
- Not treated with study drug (identified as subjects with missing study drug start date)
 - Reasons for discontinuation (i.e., not completing the DBT Phase), including not reported

6.2.3.3 Subject Disposition During the DBT Phase

The frequency table of subject disposition during the DBT Phase is provided by treatment group and overall for the DBT safety analysis set based on the DB Subject Status CRF, and displays the following categories:

- Ongoing in the DBT Phase. These are identified as subjects with (1) missing response to the question "Did the subject complete the DBT Phase?" and (2) missing DB study drug last date. This category only exists before all subjects have discontinued the DBT Phase (a milestone identified by the sponsor study management team); otherwise, subjects with missing response are categorized as "Did not complete the DBT Phase".
- Completed the DBT Phase. These are identified as subjects with (1) "yes" response to the question "Did the subject complete the DBT Phase?" and (2) nonmissing DB study drug last date)
- Did not complete the DBT Phase. These are identified as subjects with (1) "no" or missing response to the question "Did the subject complete the DBT Phase?" and (2) nonmissing DB study drug last date.
 - Reasons for not completing the DBT Phase, including not reported
- Continued to the next phase. These are identified as subjects with "yes" response to the question "Will the subject continue into the next phase of the study?".
 - o Next phase, i.e., OLE or Follow-Up

- Did not continue to the next phase. These are identified as subjects with "no" response to the question "Will the subject continue into the next phase of the study?". Subjects with missing response to this question are included only after all subjects have discontinued the DBT Phase.
 - Reasons for not continuing to the next phase, including not reported.

6.2.3.4 Subject Disposition During the OLE Phase

The frequency table of subject disposition during the OLE Phase is provided by treatment group/OL rimegepant and overall for the OL rimegepant safety analysis set based on the OLE Subject Status CRF, and displays the following categories:

- Ongoing in the OLE Phase. These are identified as subjects with (1) missing response to the question "Did the subject complete the OLE Phase?" and (2) missing OL rimegepant last date. This category only exists before the LSLV database lock; otherwise, subjects with missing response are categorized as "Did not complete the OLE Phase".
- Completed the OLE Phase. These are identified as subjects with (1) "yes" response to the question "Did the subject complete the OLE Phase?" and (2) nonmissing OL rimegepant last date)
- Did not complete the OLE Phase. These are identified as subjects with (1) "no" response to the question "Did the subject complete the OLE Phase?" and (2) nonmissing OL rimegepant last date. Subjects with missing response to this question are included only after the LSLV database lock.
 - Reasons for not completing the OLE Phase, including not reported
- Continued to the Follow-Up Phase. These are identified as subjects with "yes" response to the question "Will the subject continue to the Follow-Up Phase?".
- Did not continue to the Follow-Up Phase. These are identified as subjects with "no" response to the question "Will the subject continue to the Follow-Up Phase?"). Subjects with missing response to this question after the LSLV database lock are also included.
 - o Reasons for not continuing to the next phase, including not reported.

6.2.3.5 Subject Disposition During the Follow-Up Phase

The frequency table of subject disposition during the Follow-Up Phase is provided by treatment group/OL rimegepant status and overall for the follow-up safety analysis set based on the Follow-Up Subject Status CRF, and displays the following categories:

- Did not formally enter the Follow-Up Phase. These are identified as subjects with missing response to the question "Did the subject complete the Follow-Up Phase?", and either of the following:
 - o "No" response to the question "Will the subject continue to the Follow-Up Phase?" on the OLE Subject Status CRF

o "No" response to the question "Will the subject continue into the next phase of the study?" on the DB Subject Status CRF.

A footnote explains that these are subjects with data in the follow-up safety analysis period who did not continue to the Follow-Up Phase as per DB or OLE Subject Status CRF.

- Ongoing in the Follow-Up Phase. These are identified as subjects with missing response to the question "Did the subject complete the Follow-Up Phase?" and who are not already categorized as "Did not formally enter the Follow-Up Phase".
 - This category only exists before the LSLV database lock. After the LSLV database lock, these subjects are categorized as "Did not complete the Follow-Up Phase".
- Completed the Follow-Up Phase. These are identified as subjects with "yes" response to the question "Did the subject complete the Follow-Up Phase?"
- Did not complete the Follow-Up Phase. These are identified as subjects with "no" response to the question "Did the subject complete the Follow-Up Phase?".
 - o Reasons for not completing the Follow-Up Phase, including not reported.

6.2.4 Protocol Deviations

6.2.4.1 Relevant Protocol Deviations

The frequency table of relevant protocol deviations is provided by treatment group and overall for the full analysis set by deviation type (eligibility, subject management), category, and subcategory in the order specified in Section 9.1. Results for all relevant protocol deviation categories and subcategories are displayed, even those with 0 counts, unless otherwise specified.

The by-subject listing of relevant protocol deviations is provided for the full analysis set. This includes deviation type, category, and subcategory, which are additional sorting variables.

6.2.4.2 Significant Protocol Deviations

The by-subject listing of significant protocol deviations is provided for the full analysis set, and is based on the Protocol Deviations CRF. This includes date deviation occurred, violation code, inclusion/exclusion number, and description, which are additional sorting variables. Significant protocol deviations are defined as those with a "yes" response to the question "Is the deviation significant?". A footnote describes the raw data source and how significant protocol deviations are identified as "Significant protocol deviations are those reported as significant by sites on the Protocol Deviations CRF.".

6.2.5 Baseline Characteristics

Baseline characteristics include (1) demographics and other relevant baseline characteristics, (2) baseline disease characteristics (i.e., migraine history, cardiac and other risk factors, and efficacy during the OP), (3) medical history, and (4) nonstudy prior medications. These are detailed in Sections 6.2.5.1 through 6.2.5.4, respectively.

Tables of baseline characteristics are provided for the following analysis sets:

- Migraine analysis set: baseline characteristics (1) and (2) by treatment group and overall to support efficacy
- DBT safety analysis set: baseline characteristics (1) through (4) by treatment group and overall to support DBT safety
- OL rimegepant safety analysis set: demographics and other relevant baseline characteristics by treatment group/OL rimegepant and overall to support OL rimegepant safety
- DB or OL rimegepant safety analysis set: demographics and other relevant baseline characteristics by treatment group/OL rimegepant and overall to support DB or OL rimegepant safety

The frequency cross table of randomization stratum (i.e., use of previous prophylactic migraine medication generally considered to have efficacy [yes, no]) from IWRS versus actual data is provided for the full analysis set by treatment group and overall. See Section 6.2.5.4.

Baseline for a parameter (e.g., weight) is defined according to analysis set; refer to the Core SAP for details, including handling of ties on the same measurement date (entry date/time is the "earliest data creation time" variable in the raw CRF datasets). Note that the baseline value of a parameter is independent of the baseline analysis visit defined in Table 5; the latter is used only in by-subject listings that display visit.

By-subject listings are provided for the enrolled analysis set for the following: demographics; medical history; and migraine history.

6.2.5.1 Demographics and Other Relevant Baseline Characteristics

Refer to the Core SAP for the table of demographics and other relevant characteristics. Other relevant characteristics also include the following:

- Previous study participation (e.g., any study, BHV3000-301, BHV3000-302, BHV3000-303, etc.)
- Randomization stratum based on actual data use of previous prophylactic migraine medication generally considered to have efficacy: yes, no (see Section 6.2.5.4).

Note that race and ethnicity are summarized only for subjects in the United States of America, and percentages are calculated against the number of subjects in the United States of America.

6.2.5.2 Baseline Disease Characteristics

Migraine History

Refer to the Core SAP for the table of migraine history.

Cardiac and Other Risk Factors

Refer to the Core SAP for the frequency table of cardiac and other risk factors. This table is provided only for the DBT safety analysis set.

Migraine-Related Event Days During the OP

The table of migraine-related event days per month during the OP is provided only for the migraine analysis set, and summarizes the following efficacy parameters descriptively as continuous or categorical variables during the OP analysis period:

- Migraine days per month by pain intensity (total; moderate or severe). Categories are $< 6, \ge 6$ to $< 8, \ge 8$ to $< 12, \ge 12$.
- Headache days per month by pain intensity (total; moderate or severe). Categories are same as for migraine days per month above.
- Acute migraine-specific medication days per month. Categories are 0, > 0 to < 2, ≥ 2 to < 4, ≥ 4 to < 6, ≥ 6 to < 8, ≥ 8 to ≤ 14, > 14. Acute migraine medication days per month. Categories are the same as for acute migraine-specific medication days per month, listed above. The table of migraine related event days per week during the OP is provided only for the first month migraine analysis set, and summarizes the following efficacy parameters descriptively as continuous or categorical variables during the OP analysis period:
- Migraine days per week by pain intensity (total; moderate or severe). Categories are $< 1, \ge 1$ to $< 2, \ge 2$ to $< 3, \ge 3$.
- Headache days per week by pain intensity (total; moderate or severe). Categories are same as for migraine days per week above.

See Section 6.3.1 for migraine days per month, Section 6.3.3.1 for headache days per month, Section 6.3.3.3 for migraine days per week and headache days per week, Section 6.3.2.2 for acute migraine-specific medication days per month, Section 6.3.3.6 for acute migraine medication days per month, and Section 7.2 for the OP analysis period.

Categories may be redefined or combined based on the availability of the data.

6.2.5.3 Medical History

The frequency table of medical history is provided by system organ class (SOC) and preferred term (PT), and is displayed in descending order of overall frequency within SOC and PT.

The frequency table of medical history of hypertension by SOC and PT is also provided.

6.2.5.4 Nonstudy Prior Medications

Frequency tables of the following nonstudy medications are provided by therapeutic class and preferred name:

- Previous medications for migraine prevention generally considered to have efficacy
- Previous prophylactic migraine medications
- Current medications: all; acute migraine

Medications are displayed in descending order of overall frequency within therapeutic class and preferred name. See also Section 6.2.6.3 for the definitions of acute migraine and prophylactic migraine medications.

Medications for migraine prevention generally considered to have efficacy are defined as nonstudy medications with preferred names containing any preferred name listed in the latest version of the sponsor-provided file Medications for Migraine Prevention Generally Considered to Have Efficacy.xlsx or equivalent.

Refer to the Core SAP for the definitions of previous and current medication types.

6.2.6 Exposure

See Section 7.1 for derived dates.

6.2.6.1 Study Medication

Study drug is dispensed in a wallet-type blister card with a unique wallet ID. Each wallet has 8 tablets. During the DBT Phase, each wallet contains only rimegepant, only matching placebo, or alternating rimegepant and matching placebo depending on the randomization. During the OLE Phase, each wallet contains only rimegepant. Sites report the wallet ID, study medication start date, study medication end date, and number of tablets taken per day on the IP Dosing CRF.

The kit type identifier associated with a wallet ID is DB rimegepant EOD/placebo EOD, DB rimegepant QD, DB placebo QD, or OL rimegepant, and is obtained by merging the IP Dosing CRF data with the DB study drug kit list file data and OL rimegepant kit list file data by wallet ID. Wallet IDs are 5 digits for DB study drug and 6 digits for OL rimegepant.

The by-subject listing of study drug is provided for the safety analysis set, and presents study medication start date, study medication end date, study day derived from study medication start date, number of tablets taken per day ≥ 0 , wallet ID, and kit type identifier. The listing also displays DB study drug start and end dates, OL rimegepant start and end dates , displays rimegepant exposure parameters (time on DBT, time on OL rimegepant, time on DB or OL rimegepant), and identifies invalid wallet IDs. Valid DB wallet IDs are those in the DB study drug kit list file. Valid OL wallet IDs are those in the OL rimegepant kit list file. The listing is sorted by site-subject ID, study medication start date, study medication end date, and wallet ID.

DB Study Drug Exposure

The table of DB study drug exposure is provided by treatment group for the DB study drug safety analysis set, and summarizes the following parameters descriptively as continuous or categorical variables:

- Time on DB study drug (weeks), derived as (DB study drug end date DB study drug start date + 1)/7
- Time on DB study drug (weeks) categories: $< 2, \ge 2$ to $< 4, \ge 4$ to $< 6, \ge 6$ to $< 8, \ge 8$ to $< 10, \ge 10$ to $< 12, \ge 12$
- Cumulative DB study drug exposure (mg), derived by summing {number of days × number of tablets taken per day × dose} across records with complete study medication start date and valid DB wallet ID.
 - Number of days for a record is derived as imputed study medication end date study medication start date + 1.
 - o If the kit type identifier is DB rimegepant EOD/placebo EOD, then the dose is 37.5 mg.
 - If the kit type identifier is DB rimegepant QD, then the dose is 75 mg.
 - Otherwise, the dose is 0.
- Average DB study drug exposure (mg per day), derived as cumulative DB study drug exposure/time on DB study drug (days)
- Total DB study drug exposure (tablets) summed across all subjects, derived by summing cumulative DB exposure across all subjects
- Total DB study drug exposure (patient-years), derived by summing (DB study drug end date
 DB study drug start date + 1)/365.25 across all subjects.

OL Rimegepant Exposure

The table of OL rimegepant exposure is provided by treatment group and overall for the OL rimegepant safety analysis set, and summarizes the following parameters descriptively as continuous or categorical variables:

- Time on OL rimegepant (weeks), derived as (OL rimegepant end date OL rimegepant start date + 1)/7
- Time on OL rimegepant (weeks) categories: $< 2, \ge 2$ to $< 4, \ge 4$ to $< 6, \ge 6$ to $< 8, \ge 8$ to $< 10, \ge 10$ to $< 12, \ge 12$
- Cumulative OL rimegepant exposure (mg), derived by summing {number of days × number of tablets taken per day × 75} across records with complete study medication start date and valid OL wallet ID
- Average OL rimegepant exposure (mg per day), derived as cumulative OL rimegepant exposure/time on OL rimegepant (days)

- Total OL rimegepant exposure (tablets) summed across all subjects, derived by summing cumulative DB exposure across all subjects
- Total OL rimegepant exposure (patient-years), derived by summing (OL rimegepant end date
 OL rimegepant start date + 1)/365.25 across all subjects.

DB or **OL** Rimegepant Exposure

The table of DB or OL rimegepant exposure is provided by treatment group and overall for the DB or OL rimegepant safety analysis set, and summarizes the following parameters descriptively as continuous or categorical variables:

- Time on DB or OL rimegepant (weeks), derived as (DB or OL rimegepant end date DB or OL rimegepant start date + 1)/7
- Time on DB or OL rimegepant (weeks) categories: $< 2, \ge 2$ to $< 4, \ge 4$ to $< 8, \ge 8$ to $< 12, \ge 12$ to $< 16, \ge 16$ to $< 20, \ge 20$ to $< 24, \ge 24$
- Time on DB or OL rimegepant milestone categories:
 - \circ \geq 3 months, defined as \geq 11 weeks
 - \circ \geq 6 months, defined as \geq 23 weeks.
- Cumulative DB or OL rimegepant exposure (mg), derived by summing {number of days × number of tablets taken per day × dose} across records with complete study medication start date and kit type identifier of DB rimegepant EOD/placebo EOD, DB rimegepant QD, or OL rimegant.
 - o If the kit type identifier is DB rimegepant EOD/placebo EOD, then the dose is 37.5 mg.
 - o If the kit type identifier is DB rimegepant QD or OL rimegepant, then the dose is 75 mg.
- Average DB or OL rimegepant exposure (mg per day), derived as cumulative DB or OL rimegepant exposure/time on DB or OL rimegepant (days)
- Total DB or OL rimegepant exposure (tablets) summed across all subjects, derived by summing cumulative DB exposure across all subjects
- Total DB or OL rimegepant exposure (patient-years), derived by summing (DB or OL rimegepant end date DB or OL rimegepant start date + 1)/365.25 across all subjects.

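### SAP 6.2.6.1 builds the open-label and combined tablet totals from double-blind exposure, and appears to sum milligrams into rows labelled tablets

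*SAP*

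**What the plan says.** SAP section 6.2.6.1 (Study Medication) describes three exposure tables: double-blind (DB) study drug, open-label (OL) rimegepant, and DB or OL rimegepant combined. Each has a row for total tablets across subjects:

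- DB table: "Total DB study drug exposure (tablets) summed across all subjects, derived by summing cumulative DB exposure across all subjects"
- OL table: "Total OL rimegepant exposure (tablets) summed across all subjects, derived by summing cumulative DB exposure across all subjects"
- Combined table: "Total DB or OL rimegepant exposure (tablets) summed across all subjects, derived by summing cumulative DB exposure across all subjects"

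The label changes from row to row, but the derivation does not.

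The DB quantity defined in that section is "Cumulative DB study drug exposure (mg), derived by summing {number of days × number of tablets taken per day × dose", so it is in mg. The dose factor varies with the kit. The rule for the every-other-day wallets is "If the kit type identifier is DB rimegepant EOD/placebo EOD, then the dose is 37.5 mg". Daily wallets carry a factor of 75 mg, and placebo wallets fall under the closing rule, "Otherwise, the dose is 0". Cumulative OL exposure and cumulative combined exposure have their own definitions, also in mg, but the tablet rows do not use them. Tablet counts without a dose factor appear only in section 6.2.6.2, where they serve the compliance calculation. The tablet rows do not refer to them.

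**The concern.** Two things look wrong.

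- **Phase.** The OL and combined rows are told to add up DB exposure. The neighbouring rows in the same tables (cumulative mg, mg per day, time on drug, patient-years) each use the correct phase, so this looks like a line copied forward from the DB table.
- **Unit.** If the phrase in the tablet rows means the cumulative DB exposure defined a few lines above, then mg are being summed under a tablets label. Because the dose factor differs by kit, the distortion would differ by arm, and the placebo arm would show no tablets at all.

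Section 8 of the SAP says that all tables described are produced for the final study report. At stake is whether one row in each of three exposure tables in that report is correct.

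**Working it through.** **Step 1: reproduce the SAP's own tablet total.** The example in SAP section 9.4 has four records with tablets taken: 1–3 January at 1 a day, 6–9 January at 1 a day, 9–11 January at 2 a day, and 13 January at 1. Tablets = sum of (days × tablets per day):

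3×1 + 4×1 + 3×2 + 1×1 = 14

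This matches the SAP's 14 tablets. The mg rule applied to the same records gives 14 × 75 = 1,050 for a daily kit, 14 × 37.5 = 525 for an every-other-day (EOD) kit, and 14 × 0 = 0 for a placebo kit.

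**Step 2: compare each row's label with what its rule sums.**

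| Row | Should count | Rule sums | Left out |
|---|---|---|---|
| DB total | DB tablets | DB exposure | nothing (unit in doubt) |
| OL total | OL tablets | DB exposure | all OL tablets |
| Combined total | DB rimegepant-kit and OL tablets | DB exposure | all OL tablets |

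**Step 3: size on the mg reading.** Inputs: 220 subjects per arm (protocol 5.1), a 12-week DB phase (84 days) with one tablet a day, and the dose factors above. Assumptions: full compliance, and all 220 per arm continue for 84 OL days (the protocol allows up to 660 in total).

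- Tablets per arm per phase: 220 × 84 = 18,480
- Rule, daily arm: 18,480 × 75 = 1,386,000
- Rule, EOD arm: 18,480 × 37.5 = 693,000
- Rule, placebo arm: 18,480 × 0 = 0

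| DB arm | DB tablets | OL tablets | Combined, rimegepant kits | Rule's value in every row |
|---|---|---|---|---|
| EOD | 18,480 | 18,480 | 36,960 or 27,720 | 693,000 |
| Daily | 18,480 | 18,480 | 36,960 | 1,386,000 |
| Placebo | 18,480 | 18,480 | 18,480 | 0 |

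The two EOD combined values are 18,480 + 18,480 = 36,960 if every wallet tablet counts, and 18,480/2 + 18,480 = 27,720 if only active tablets count. In the overall column of the OL table, the rule gives 693,000 + 1,386,000 + 0 = 2,079,000 against 3 × 18,480 = 55,440 OL tablets.

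**Step 4: size if the phrase means a DB tablet count.** The DB row is then right.

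- The combined row for the EOD and daily arms shows 18,480 against 36,960 when every wallet tablet counts, so half is missing.
- For placebo subjects who enter the extension, the tablets summed would be DB placebo tablets.
- The OL row shows 18,480, the same as the OL count, but only because both phases are assumed complete at 84 days. A subject with 84 DB tablets who stops after 28 OL tablets would contribute 84 instead of 28.

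**The case against.** **The unit error is not certain.** The mg variable has a longer name that includes the words study drug, and the average-exposure row cites it by that name. The tablet rows use a shorter phrase and are labelled tablets. The DB tablet count in 6.2.6.2 fits that label. This stands: the mg reading is an inference, and the DB row may be sound. It does not rescue the other two rows, because no reading of DB exposure includes OL tablets.

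**Other documents or checks may catch it.** The SAP sends output details to a Core SAP and a mock-output document, neither of which is available here, and draft outputs are run before database lock. This also stands: a reader might infer that the report will carry wrong totals, but the documents support only that it would if the text is programmed as written. Against that, this SAP states its own derivation. Its revision history also records edits to 6.2.6.1 in Versions 2, 4 and 6, and the line remains in Version 7.

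**The rows feed nothing else.** A reader might infer that total tablets is a safety denominator and that event rates are distorted. The documents do not support this. Exposure-adjusted adverse events (6.4.1.5) and liver-test elevations (6.4.2.2) use period start and end dates. Patient-years, mg, mg per day and time on drug are derived separately and for the correct phase. No objective or endpoint is based on total tablets.

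**Conclusion.** The point holds as a drafting error in three descriptive rows. It is certain from the text that the OL and combined tablet totals name the wrong phase: followed literally, one holds no OL tablets and the other omits the OL phase. It is likely, but inferred, that the quantity summed is in mg. The 75-fold (daily) and 37.5-fold (EOD) inflation and the zero for placebo depend on that reading. The absolute figures also assume 220 subjects per arm, 84 days in each phase, full compliance and no dropout. Efficacy tests, alpha, sample size, exposure-adjusted rates and patient-years are untouched. It should be corrected because the stated derivation is wrong and easily repaired, not because it threatens the safety conclusions.

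**What to change.** Rewrite the three rows in SAP 6.2.6.1:

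- **DB total:** sum over subjects the DB tablet count already defined in 6.2.6.2.
- **OL total:** sum over subjects the OL tablet count already defined in 6.2.6.2.
- **Combined total:** sum days × tablets per day over the DB EOD and DB daily kits plus the OL kits, and state whether the placebo tablets in EOD wallets are counted. In the illustration that choice moves the EOD figure between 36,960 and 27,720.

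If a total in mg is also wanted, give it a separate, labelled row. Check that the Core SAP and mock outputs agree with the new wording.

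The cost is three lines of text and a small programming change. The DB and OL counts are already derived for compliance, and no data collection changes. If only active tablets are to count for EOD wallets, the programming rule for identifying them must also be stated.
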